## **ABBREVIATIONS AND DEFINITIONS**

ADaM	analysis data model
AE	adverse event
ATC	anatomical therapeutic chemical
BMI	body mass index
BOR	best objective response
bpm	beats per minute
BP	blood pressure
CI	confidence interval
CR	complete response
CRF	case report form
CS	clinically significant
CTCAE	Common Terminology Criteria for Adverse Events
CV	coefficient of variation
DBP	diastolic blood pressure
DLT	dose limiting toxicity
ECG	electrocardiogram
ECHO	echocardiogram
ECOG	Eastern Cooperative Oncology Group
eCRF	electronic case report form
EDC	electronic data capture
EOS	end-of-study
FDA	Food and Drug Administration
GCP	Good Clinical Practices
HR	heart rate
ICH	International Committee for Harmonization
IP	Investigational Product
ITT	intent to treat
IU	international units
IWG	revised International Working Group Criteria
LVEF	Left ventricular ejection fraction
K-M	Kaplan-Meier
mmHg	millimeters of mercury
MedDRA	Medical Dictionary for Regulatory Activities
NCI	National Cancer Institute
MTD	maximum tolerated dose
NCS	not clinically significant
ORR	objective response rate
OS	overall survival
PD	progressive disease

---

PFS	progression free survival
PK	pharmacokinetic
PR	partial response
PT	preferred term
PPT	partial prothrombin time
QTcF	corrected QT interval (using Fridericia's correction formula)
RR	respiratory rate
SAE	serious adverse event
SAP	statistical analysis plan
SAS	Statistical Analysis Software
SBP	systolic blood pressure
SD	stable disease
SOC	system organ class
TEAE	treatment-emergent adverse event
ULN	upper limit of normal
UNK	unknown
WHO-DD	World Health Organization - Drug Dictionary

## **1. INTRODUCTION**

The Statistical Analysis Plan (SAP) describes the data analysis specifications for Sumitomo Dainippon Pharma Oncology, Inc protocol TPI-ALV-102 titled: *“A Phase 1b/2, Open-label Clinical Study to Determine Preliminary Safety and Efficacy of Alvocidib When Administered in Sequence After Decitabine or Azacitidine in Patients with MDS”*. It details the inferential statistical methodology to be used in analyzing study data and outlines the statistical programming specifications, tables, figures, and listings. It describes the variables and populations, anticipated data transformations and manipulations, and other details of the analyses not provided in the clinical study protocol.

This version of the SAP was prepared in accordance with the protocol TPI-ALV-102 Amendment 4 dated August 19, 2020. Other related documents are the annotated patient case report forms (version 23SEP2020) and the corresponding Medrio electronic data capture (EDC) data dictionary.

The SAP will be finalized prior to database lock and describes the statistical analysis as it is foreseen when the study is being planned. If circumstances should arise during the study rendering this analysis inappropriate, or if in the meantime improved methods of analysis should come to light, different analyses may be made. Any deviations from the SAP after database lock, reasons for such deviations, and all alternatives or additional statistical analyses that may be performed will be described in a SAP Addendum and in the clinical study report. This SAP supersedes the statistical considerations identified in the protocol.

**NOTE: On November 17, 2020, the investigative sites were notified of the decision by SDPO to close TPI-ALV-102 following a review of the company portfolio. This SAP will reflect the latest protocol (Amendment 4) along with the current study status where appropriate.**

**As of November 17, 2020, a total of 20 patients across 6 cohorts have enrolled. The breakout per cohort is described below:**

Cohort 1 20mg/m2 (N=3)	Cohort 2 30mg/m2 (N=3)	Cohort 3 45mg/m2 (N=3)	Cohort 4 60mg/m2 (N=4)	Cohort 5 AZA 75mg/m2 + Alvocidib (N=3)	Cohort 6 AZA 75mg/m2 + Alvocidib (N=4)	Total (N=20)
------------------------------	------------------------------	------------------------------	------------------------------	---	---	-----------------

**Efficacy endpoints will not be analyzed via inferential statistical methods due to low enrollment (sample size). Summary tables as described in this SAP and full patient listings will be provided to enable a synoptic clinical study report to be written for this study.**

## **2. OVERVIEW OF STUDY DESIGN**

### Experimental Design:

This is a Phase 1b/2, open-label, safety, efficacy, PK, and pharmacodynamic (PD) study of Alvocidib When Administered in Sequence After Decitabine or Azacitidine in Patients with MDS. There are 3 main parts of the trial:

[figure not shown]
#### Phase 1b

Patients will be enrolled in cohorts of 3-6 patients. Escalation of the alvocidib dose will follow a standard 3+3 design with sequential cohorts of 3 patients treated with incrementally higher doses of alvocidib administered in sequence after DEC (during dose escalation) or AZA until a DLT is observed and the MTD is established (as defined in Section 4.5.3 of the protocol). The first 2 patients at a dose level may be enrolled simultaneously and the third patient will be enrolled after 14 days so long as the 2 initial patients have not experienced any unacceptable toxicity.

If 1 of 3 patients in a cohort experiences a DLT, up to 3 additional patients will be treated at that dose level. If no additional DLTs are observed in the expanded 3- to 6-patient cohort within 28 days after the last patient was first dosed, the dose will be escalated in a new cohort of 3 patients. If 2 or more of 3-6 patients at a given dose level experience a DLT during the first cycle, then the MTD will have been exceeded and up to a total of 6 patients will be treated at the previous lower dose level. If 0 or 1 of 6 patients experiences a DLT at this previous lower dose level, this dose will be declared the MTD.

The MTD is defined as the dose at which  $\leq 1$  of 6 patients experience a DLT during Cycle 1 with the next higher dose having at least 2 of 3 to 6 patients experiencing a DLT during Cycle 1. Adverse events meeting the definition of DLT during Cycles 2+ will be taken into consideration when evaluating dose escalation.

Dose Escalation using the modified Fibonacci Dose Escalation Scheme:

Once the MTD or preliminary RP2D of alvocidib administered via hybrid dosing (i.e., IV bolus followed by IVI) is identified, 2 cohorts of at least 3 patients each will receive AZA followed by alvocidib administered as a 30- to 60-minute IVI.

**Current Status: As of November 17, 2020, 20 patients across 6 dose cohorts were enrolled in Phase 1b.**

#### Expansion at MTD

Once the MTD or preliminary RP2D of alvocidib administered as a 30- to 60-minute IVI is determined, up to 25 patients will be enrolled in an Expansion cohort to receive alvocidib following AZA to confirm safety, explore potential biomarkers, and evaluate potential signals of alvocidib activity. Once this Expansion cohort is completed, the study will progress to Phase 2.

**Current Status: As of November 17, 2020, zero patients were enrolled in the expansion phase.**

#### Phase 2

Using optimal dose from the Phase 1b study, initiate fixed-dose study of approximately 25 patients in Simon 2-stage minimax design.

- Stage 1: Up to 15 evaluable patients will be enrolled and treated at the RP2D identified in the Phase 1b study. Stage 2 may be initiated at any point after confirming a response (CR/CRi/CRmarrow/PR/HI) in two Stage 1 patients. If there is ≤1

responder among 15 evaluable Stage-1 patients, the study will be stopped after Stage 1.

- Stage 2: Ten patients will be enrolled to bring the total enrollment in Phase 2 (including Stage-1 patients) to 25 evaluable patients. Stage-2 patients will also receive the RP2D dose of alvocidib administered by 30- to 60-minute IVI identified in the Phase 1b study. If 6 or more responses are observed in 25 patients, the conclusion will be that the combination regimen is worthy of further investigation. When the true response rate of 30% (alternative hypothesis) is tested against the null hypothesis response rate of 10%; this design yields a Type I error rate of 0.05 and power of 80%.

Any patient who withdraws from Stage 1 or 2 for treatment-related toxicity or disease progression or dies prior to being evaluated for response will be considered a nonresponder. Patients who drop out for other reasons prior to being assessed for response will be considered unevaluable and may be replaced. Enrollment into Phase 2 may be stopped at any point once  $\geq 6$  patients have had a response to treatment, but the maximum enrollment in Phase 2 will be 25 evaluable patients.

The study may be stopped early during Phase 2 in the event of unacceptable toxicities. Early stopping rules for safety are based on a Sequential Probability Ratio Test (SPRT) with a baseline toxicity rate of 5%; an upper ceiling of unacceptable toxicity of 20% (ie, toxicities meeting one or more DLT criteria as stated in Section 4.5.3); and alpha=0.05 with power=80%.

The study will be stopped if unacceptable toxicities are observed in:

- 2 of the first 2 patients
- 3 of the first 11 patients
- 4 of the first 20 patients
- 5 of the first 29 patients (Ph 2 study to enroll maximum of 25 patients, but considering possible replacement patients).

**Current Status: As of November 17, 2020, zero patients were enrolled in Phase 2.**

Study treatment:

Patients will receive alvocidib administered in sequence after fixed doses of either DEC or AZA using a standard 3+3 design according to the dose cohort shown below.

Dose Level a	Days 1-5, Decitabine	Day 8, Alvocidib b	
	1-hr IV infusion	30-min bolus	4-hr IV infusion
1	20 mg/m 	20 mg/m 	20 mg/m 
2	20 mg/m 	30 mg/m 	30 mg/m 
3	20 mg/m 	30 mg/m 	45 mg/m 
4	20 mg/m 	30 mg/m 	60 mg/m 

a It is possible for additional and/or intermediate dose levels to be added during the course of the study.

b Alvocidib to be administered first as a 30-minute ( $\pm$ 10 minutes) IV bolus followed up to 30 minutes later by a 4-hour ( $\pm$ 15 minutes) IVI.

Two separate cohorts of patients (minimum of 6 patients; 3 per cohort) will receive AZA followed by alvocidib administered as a 30- to 60-minute IVI according to the dose cohort:

Dose Level a	Azacitidine b	Day 10, Alvocidib
	IVI or SC injection c	30- to 60-min IVI
1A	75 mg/m 	75 mg/m 
1B	75 mg/m 	90 mg/m 

a It is possible for additional and/or intermediate dose levels to be added during the course of the study.

b AZA can be administered on either a 7-day or 5-2-2 schedule.

c AZA may be given as an IVI over 10 to 40 minutes or an SC injection.

The first 2 patients at a dose level may be treated simultaneously and the third patient will be treated after 14 days so long as the initial 2 patients have not experienced any unacceptable drug-related toxicity. Once the last patient enrolled has completed Day 28 without observation of a DLT and the next higher alvocidib dose level has not yet been studied, the alvocidib dose will be increased in a new 3-patient cohort.

Number of Patients Planned and Study Duration:

- Phase 1b: Approximately 12–18 months to enroll up to 24 patients in dose escalation portion up to determination of the Maximum Tolerated Dose (MTD) and Recommended Phase 2 Dose (RP2D).

20 patients were enrolled at the time of study termination.

- Expansion at MTD: Approximately 6-8 months to enroll up to 25 patients in an Expansion cohort at MTD. Data collected from these patients will be used to confirm safety, explore potential biomarkers, and evaluate potential signals of alvocidib activity. No patients enrolled in Expansion.

- Phase 2: Approximately 18 months to enroll up to 25 patients to confirm efficacy. No patients enrolled in Phase 2.

### **3. STUDY OBJECTIVES AND ENDPOINTS**

#### **3.1 Phase 1b Primary Objective**

To determine the MTD and RP2D of alvocidib administered in sequence after decitabine (DEC) or azacitidine (AZA) in patients with previously untreated MDS and patients with MDS who have received <6 cycles of treatment with HMAs

#### **3.2 Phase 1b Secondary Objectives:**

- To determine the Complete Response Rate ([CRR]: Complete response [CR] / Complete Response with Incomplete blood count recovery [CRI] / CR in marrow / Partial Response [PR] / Hematologic Improvement [HI])
- To determine if treatment with alvocidib administered in sequence after DEC (during dose escalation) or AZA results in improvements in transfusion dependence (defined as an average transfusion requirement of  $\geq 2$  units/28 days of RBCs without any consecutive 28-day gaps between transfusions for a minimum of 56 days immediately preceding first dose) and/or hemoglobin level (transfusion data to include the hemoglobin value for which the transfusion was administered and must have been  $\leq 10.0$  g/dL within 7 days prior to transfusion administration to be counted toward the RBC transfusion-dependent status):
  - Hemoglobin increase of  $\geq 1.5$  g/dL without erythropoietin-stimulating agents (ESAs)

OR

- Reduction of  $\geq 4$  RBC transfusions/8 weeks in comparison to pre-treatment values and lasting at least 8 weeks

#### **3.3 Phase 1b Exploratory Objectives**

- To evaluate MCL-1 dependence in untreated MDS patients via BH3 profiling
- To determine whether DEC (during dose escalation) or AZA treatment modulates MCL-1 dependence in peripheral blood

### **3.4 Phase 2 Primary Objective**

To determine preliminary efficacy and anti-MDS activity of alvocidib administered in sequence after AZA in untreated patients with de novo or secondary MDS

### **3.5 Phase 2 Secondary Objectives:**

- To assess the ORR per the revised International Working Group (IWG) Criteria
- To evaluate the tolerability of alvocidib when administered in sequence following AZA in this patient population
- To determine whether a defined BH3 profile predicts response to alvocidib administered in sequence after AZA in untreated MDS population
- To determine if treatment with alvocidib administered in sequence after AZA results in improvements in transfusion dependence (defined as an average transfusion requirement of  $\geq 2$  units/28 days of RBCs without any consecutive 28-day gaps between transfusions for a minimum of 56 days immediately preceding first dose) and/or hemoglobin level (transfusion data to include the hemoglobin value for which the transfusion was administered and must have been  $\leq 10.0$  g/dL within 7 days prior to transfusion administration to be counted toward the RBC transfusion-dependent status):
  - Hemoglobin increase of  $\geq 1.5$  g/dL without ESAs

OR

- Reduction of  $\geq 4$  RBC transfusions/8 weeks in comparison to pre-treatment values and lasting at least 8 weeks

### **3.6 Phase 2 Exploratory Objectives:**

- To assess the pharmacokinetics (PK) of alvocidib when administered in sequence after AZA
- To evaluate correlative biomarkers of therapy including, but not limited to, BH3 profiling with an emphasis on MCL-1 dependence, genetic mutations, and other biomarkers associated with MDS
- To document the percentage of patients transplanted post-treatment and outcomes post-transplant

- Additional exploratory analyses may be performed if useful in the interpretation of the data.

### **3.7 Study Endpoints**

#### **3.7.1 Safety Endpoints**

##### Phase 1b

Safety and tolerability of alvocidib when administered in sequence after DEC (during dose escalation) or AZA will be assessed by analyzing DLTs, MTD, and incidence rates of treatment-emergent adverse events (TEAEs) summarized within treatment group(s) at the MedDRA preferred term and primary system organ class levels. Similar summaries will be made for subsets of AEs such as (1) those judged by the Investigator to be related to study treatment, and (2) serious adverse events (SAEs). Adverse events will be graded according to NCI CTCAE v5.0. Mortality (all causes) will be calculated

Other routine safety assessments (i.e., physical examinations, vital sign measurements, and clinical laboratory testing (hematology and chemistry) will be evaluated as measures of safety and tolerability for the entire study duration. These assessments will be summarized by shift tables and treatment group using mean, standard deviation, median, minimum and maximum changes from baseline values.

##### Phase 2

During the Phase 2 study, tolerance and toxicity will be assessed through evaluation of physical examinations, vital signs, laboratory studies, solicited and unsolicited adverse events, and all causes of mortality at 30 and 60 days.

Routine safety assessments will be summarized by shift tables using mean, standard deviation, median, minimum and maximum changes from baseline values.

#### **3.7.2 Efficacy Endpoints**

##### Phase 2

###### **Primary Efficacy Endpoints**

- Assess preliminary efficacy, as determined by response rate, duration of response, hematological improvement, rate of transfusion independence, time to acute myeloid leukemia (AML), and overall survival (OS).

Efficacy endpoints will be any objective response to study drug therapy using assessments defined by the 2006 revised International Working Group (IWG) and European MDS Working Group.

#### Secondary Efficacy Endpoints

- The proportion of MDS patients in the overall population achieving RBC transfusion independence with duration  $\geq 84$  days (12 weeks) during treatment. Baseline RBC transfusion dependency is defined as an average transfusion requirement of  $\geq 2$  units/28 days of RBCs without any consecutive 28-day gaps between transfusions for a minimum of 56 days immediately preceding first dose. Transfusion data include the hemoglobin value for which the transfusion was administered and must have been  $\leq 10.0$  g/dL within 7 days prior to transfusion administration to be counted toward the RBC transfusion-dependent status.
- Platelet transfusion independence with duration  $\geq 84$  days (12 weeks) will be assessed in the proportion of patients who were platelet transfusion-dependent at baseline. Baseline platelet transfusion requirements are established by the number of platelet transfusions administered during the 56 days immediately preceding and including the date of first dose.
- Erythroid hematologic improvement and platelet hematologic improvement will be assessed according to the 2006 revised IWG criteria.
- Correlation of complete response rates with BH3 profiling results including MCL-1 dependency
- Overall survival compared to historical survival

#### **3.7.3 Pharmacokinetic (PK) Endpoints**

PK parameters will include maximum plasma concentration ( $C_{max}$ ), time to maximum concentration ( $t_{max}$ ), area under the curve from time 0 to 24 hours ( $AUC_{0-24}$ ) area under the curve from time 0 to infinity ( $AUC_{0-inf}$ ), half-life ( $t_{1/2}$ ) and clearance (CL). The PK parameters will be estimated using standard noncompartmental methods and according to FDA guidance.

#### **3.7.4 Pharmacodynamic (PD) Endpoints**

Peripheral blood and bone marrow samples will be collected at protocol-specific time points to assess the effects of alvocidib when administered in sequence after DEC (during dose escalation) or AZA. Analyses may include, but are not limited to, assessment of BH3

profiling by flow cytometry with an emphasis on MCL-1 dependence, evaluating genetic mutations, and other biomarkers associated with MDS.

#### **4. SAMPLE SIZE JUSTIFICATION**

##### Part 1b Dose Escalation

Patients will be enrolled in cohorts of 3-6 patients. Escalation of the alvocidib dose will follow a standard 3+3 design with sequential cohorts of 3 patients treated with incrementally higher doses of alvocidib until a DLT is observed and the MTD is established (Section 4.5.3). Per the standard oncology 3+3 Phase 1 dose escalation design, the total number of patients to be enrolled cannot be precisely determined as the sample size is dependent upon the observed safety profile, which will determine the number of patients per dose cohort, as well as the number of dose escalations required to achieve the MTD. It is anticipated that a maximum of 24 patients will be required to reach MTD and determine the RP2D

##### Dose Expansion at MTD

Once the MTD or preliminary RP2D of alvocidib administered by 30- to 60-minute IVI is determined, up to 25 patients will be enrolled in an Expansion cohort to receive alvocidib following either DEC or AZA to confirm safety, explore potential biomarkers, and evaluate potential signals of alvocidib activity. Once this Expansion cohort is completed, the study will progress to Phase 2.

##### Phase 2

The statistical power calculations for Phase 2 are based on the Simon 2-stage minimax design.

- Stage 1: Up to 15 evaluable patients will be enrolled and treated at the RP2D identified in the Phase 1b study. Stage 2 may be initiated at any point after confirming a response (CR/CRi/CRmarrow/PR/HI) in two Stage 1 patients. If there is  $\leq 1$  responder among 15 evaluable Stage-1 patients, the study will be stopped after Stage 1.
- Stage 2: Ten patients will be enrolled to bring the total enrollment in Phase 2 (including Stage-1 patients) to 25 evaluable patients. Stage-2 patients will also receive the RP2D dose of alvocidib administered by 30- to 60-minute IVI identified in the Phase 1b study. If 6 or more responses are observed in 25 patients, the conclusion will be that the combination regimen is worthy of further investigation. When the true response rate of 30% (alternative hypothesis) is tested against the null

hypothesis response rate of 10%; this design yields a Type I error rate of 0.05 and power of 80%.

Any patient who withdraws from Stage 1 or 2 for treatment-related toxicity or disease progression or dies prior to being evaluated for response, they will be considered a non-responder. Patients who drop out for other reasons prior to being assessed for response will be considered unevaluable and may be replaced. Enrollment into Phase 2 may be stopped at any point once  $\geq 6$  patients have had a response to treatment, but the maximum enrollment in Phase 2 will be 25 evaluable patients.

#### Phase 2 Stopping Rules based on Safety

The study may be stopped early during Phase 2 in the event of unacceptable toxicities. Early stopping rules for safety are based on a Sequential Probability Ratio Test (SPRT) with a baseline toxicity rate of 5%; an upper ceiling of unacceptable toxicity of 20% (i.e., toxicities meeting one or more DLT criteria as stated in Section 4.5.3); and alpha=0.05 with power=80%.

The study will be stopped if unacceptable toxicities are observed in:

- 2 of the first 2 patients
- 3 of the first 11 patients
- 4 of the first 20 patients
- 5 of the first 29 patients (Ph 2 study to enroll maximum of 25 patients, but considering possible replacement patients).

**Note: As of the study termination date of November 17, 2020; 20 patients have enrolled into this study.**

## **5. RANDOMIZATION, BLINDING, AND REPLACEMENT OF PATIENTS**

This is an open-label study with the identity of the treatment known to the patients, Investigators, and Sponsor; therefore, no randomization or blinding procedures will be performed.

All patients will receive study drug according to the dose cohort in which they are enrolled. Patients will be enrolled into open dosing cohorts from all participating centers. The study will be managed by the Sponsor and/or its designee and all sites must receive authorization from the Medical Monitor for enrollment of any eligible patient.

Patients who are lost to follow-up or withdraw consent for study participation prior to administration of study drug may be replaced, at sponsor's discretion.

## **6. DEFINITIONS OF PATIENT POPULATIONS TO BE ANALYZED**

his study will have three analysis populations:

- Intent-to-Treat (ITT) analysis set includes all patients who were enrolled into the study.
- Safety analysis set consists of all patients who received any amount of study treatment.
- Response Evaluable set consists of patients who have at least one post-baseline efficacy assessment; patients without a post-baseline efficacy assessment will not be considered evaluable for the primary efficacy analysis. Patients who discontinue due to disease progression or die or treatment-related toxicity prior to having a disease assessment will be included in the Response Evaluable population.

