- Stage 1: Up to 15 evaluable patients will be enrolled and treated at the RP2D identified in the Phase 1b study. Stage 2 may be initiated at any point after confirming a response (CR/CRI/CRmarrow/PR/HI) in two Stage 1 patients. If there is ≤ 1 responder among 15 evaluable Stage-1 patients, the study will be stopped after Stage 1.
- Stage 2: Ten patients will be enrolled to bring the total enrollment in Phase 2 (including Stage-1 patients) to 25 evaluable patients. Stage-2 patients will also receive the RP2D dose of alvocidib administered by **30- to 60-minute** IVI identified in the Phase 1b study. If 6 or more responses are observed in 25 patients, the conclusion will be that the combination regimen is worthy of further investigation. When the true response rate of 30% (alternative hypothesis) is tested against the null hypothesis response rate of 10%; this design yields a Type I error rate of 0.05 and power of 80%.

Any patient who withdraws from Stage 1 or 2 for treatment-related toxicity or disease progression, or dies prior to being evaluated for response will be considered a nonresponder. Patients who drop out for other reasons prior to being assessed for response will be considered unevaluable and may be replaced. Enrollment into Phase 2 may be stopped at any point once ≥ 6 patients have had a response to treatment, but the maximum enrollment in Phase 2 will be 25 evaluable patients.

The study may be stopped early during Phase 2 in the event of unacceptable toxicities. Early stopping rules for safety are based on a Sequential Probability Ratio Test (SPRT) with a baseline toxicity rate of 5%; an upper ceiling of unacceptable toxicity of 20% (ie, toxicities meeting one or more DLT criteria as stated in [Section 4.5.3](#)); and alpha=0.05 with power=80%.

The study will be stopped if unacceptable toxicities are observed in:

- 2 of the first 2 patients
- 3 of the first 11 patients
- 4 of the first 20 patients
- 5 of the first 29 patients (Ph 2 study to enroll maximum of 25 patients, but considering possible replacement patients)

Safety Assessments

Incidence rates of treatment-emergent adverse events (TEAEs) will be summarized within treatment group at the Medical Dictionary for Regulatory Activities (MedDRA) preferred term and primary system organ class levels.

Similar summaries will be made for subsets of adverse events (AEs) such as (1) those judged by the Investigator to be related to study treatment, and (2) serious adverse events (SAEs).

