4.4.2.1 Phase 1b: Dose-escalation

Patients will receive alvocidib administered in sequence after fixed doses of either DEC or AZA using a standard 3+3 design according to the dose cohorts in *Table 5* and *Table 6*.

Table 5: Proposed Dose Escalation Schema (DEC + Alvocidib)

Dose Level ^a	Days 1-5, Decitabine	Day 8, Alvocidib ^b	
	1-hr IV infusion	30-min bolus	4-hr IV infusion
1	20 mg/m ²	20 mg/m ²	20 mg/m ²
2	20 mg/m ²	30 mg/m ²	30 mg/m ²
3	20 mg/m ²	30 mg/m ²	45 mg/m ²
4	20 mg/m ²	30 mg/m ²	60 mg/m ²

a It is possible for additional and/or intermediate dose levels to be added during the course of the study.

b Alvocidib to be administered first as a 30-minute (\pm 10 minutes) IV bolus followed up to 30 minutes later by a 4-hour (\pm 15 minutes) IVI.

Two separate cohorts of patients (minimum of 6 patients; 3 per cohort) will receive AZA followed by alvocidib administered as a **30- to 60-minute** IVI according to the dose cohorts in **Table 6**.

Table 6: Proposed Dose Schema (AZA + Alvocidib)

Dose Level ^a	Azacitidine ^b	Day 10, Alvocidib
	IVI or SC injection ^c	30- to 60-min IVI
1A	75 mg/m ²	75 mg/m ²
1B	75 mg/m ²	90 mg/m ²

a It is possible for additional and/or intermediate dose levels to be added during the course of the study.

b AZA can be administered on either a 7-day or 5-2-2 schedule.

c AZA may be given as an IVI over 10 to 40 minutes or an SC injection.

The first 2 patients at a dose level may be treated simultaneously and the third patient will be treated after 14 days so long as the initial 2 patients have not experienced any unacceptable drug-related toxicity. Once the last patient enrolled has completed Day 28 without observation of a DLT and the next higher alvocidib dose level has not yet been studied, the alvocidib dose will be increased in a new 3-patient cohort.

If 1 of 3 patients in a cohort experiences a DLT, up to 3 additional patients will be treated at that dose level. If no additional DLTs are observed in the expanded 3- to 6 patient cohort within 28 days after the last patient was first dosed, the dose will be escalated in a new cohort of 3 patients. If 2 or more of 3-6 patients at a given dose level experience a DLT during the first cycle, then the MTD will have been exceeded and up to a total of 6 patients will be treated at the previous lower dose level. If 0 or 1 of 6 patients experiences a DLT at this previous lower dose level, this dose will be declared the MTD.

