11.4 ANALYSIS POPULATION SETS

This study will have three analysis populations:

- **Intent-to-Treat (ITT)** analysis set includes all patients who were enrolled into the study.
- **Safety Analysis Set** consists of all patients who received study treatment (alvocidib).
- **Response Evaluable Set** consists of patients who have at least one post-baseline efficacy assessment; patients without a post-baseline efficacy assessment will not be considered evaluable for the primary efficacy analysis. Patients who discontinue due to disease progression or die or treatment-related toxicity prior to having a disease assessment will be included in the Response Evaluable population.

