**NOTE: due to the study status, the safety population will be used for all summary tables.**

## **7. PLANNED ANALYSES**

### **7.1 Interim Analysis**

For Phase 1b and dose expansion, safety data will be monitored continuously per standard Phase 1 oncology study practices.

For Phase 2, because the Simon 2-stage minimax design will be employed, response rate data will be assessed after Stage 1 and Stage 2 have been enrolled.

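### No DLT-evaluable set is defined and the two Safety sets conflict, so a patient who stops after DEC or AZA but before alvocidib could be counted as a DLT non-event.

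*SAP*

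**What the plan says.** **Analysis sets.** Protocol Section 11.4 and SAP Section 6 each define three sets: ITT, Safety and Response Evaluable. Neither defines a set for DLT evaluation.

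**Safety set.** In the protocol it "consists of all patients who received study treatment (alvocidib", the bracket naming the qualifying drug. Protocol Section 11.10 likewise limits safety summaries to patients given any alvocidib. In SAP Section 6 the "Safety analysis set consists of all patients who received any amount of study treatment", so one dose of DEC or AZA is enough. The note closing that section adds that "due to the study status, the safety population will be used for all summary tables", and SAP Section 12 applies the set to all safety analyses. SAP Section 3.7.1 lists DLTs and MTD among the safety endpoints.

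**Timing.** Protocol Section 4.4.2 gives DEC on Days 1-5 with alvocidib on Day 8, or AZA from Day 1 with alvocidib on Day 10. Protocol Section 4.5.3 assesses DLTs during Cycle 1.

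**Escalation.** Protocol Section 4.4.2.1: "If 1 of 3 patients in a cohort experiences a DLT, up to 3 additional patients will be treated at that dose level". Its Day 28 completion condition names only the last patient enrolled.

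**Replacement.** SAP Section 5: "Patients who are lost to follow-up or withdraw consent for study participation prior to administration of study drug may be replaced", at the sponsor's discretion. The other rule, "Patients who drop out for other reasons prior to being assessed for response will be considered unevaluable and may be replaced", is part of the Phase 2 response design (Protocol Section 4.1).

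**The concern.** For at least a week of Cycle 1 a patient has had the hypomethylating agent but not the drug whose dose is being tested. Someone who leaves in that interval says nothing about the toxicity of the alvocidib level. A 3+3 rule decides on zero, one or two events in very small denominators, so one uninformative patient scored as a non-event makes a dose look safer than the data show.

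A DLT-evaluable definition normally prevents this, and here there is none. The only general-purpose set that could stand in for it has two definitions, one admitting the patient and one not. Protocol Section 11.1 says SAP changes to the planned analysis will be clearly documented; SAP Section 16 lists none and says the SAP supersedes the protocol's statistical considerations. MTD and RP2D are the Phase 1b primary objective, so the ambiguity falls on the main Phase 1b result.

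**Working it through.** **1. Can the patient be counted?**

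| Question | Points towards counting | Points away |
|---|---|---|
| In the Safety set? | SAP 6 and 12: any study treatment | Protocol 11.4 and 11.10: alvocidib required |
| In the 3+3 cohort? | No exposure or follow-up minimum anywhere; Day 28 condition names only the last patient | Protocol 4.1 describes cohorts as treated with alvocidib doses; 11.10 gives the escalation committee the safety profiles of alvocidib recipients |
| Not replaceable? | Protocol 5.1.2 and SAP 8.6 tie first study drug to Day 1, i.e. DEC or AZA | Protocol 9.1 calls alvocidib the investigational study drug |

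The text neither requires nor excludes counting.

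**2. Size if one of the first three is counted.** The documents state no operating characteristic for the 3+3 rule, so there is no planned figure to reproduce. Inputs: the escalation rule (Protocol 4.4.2.1) and a true DLT rate *p*. The documents do not give *p* for Phase 1b; I assume 10% to 50%. The 20% value matches the unacceptable-toxicity ceiling of the Phase 2 safety rule. I assume an unexposed patient cannot have a DLT and that the three added patients are all exposed.

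- All three exposed: P(pass) = (1−p)³ + 3p(1−p)² × (1−p)³
- One of three unexposed, scored as a non-event: P(pass) = (1−p)² + 2p(1−p) × (1−p)³

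At p = 0.30: 0.343 + 0.441 × 0.343 = 0.494, against 0.490 + 0.420 × 0.343 = 0.634.

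| True DLT rate | All exposed | One unexposed | Difference |
|---|---|---|---|
| 10% | 0.906 | 0.941 | 0.035 |
| 20% | 0.709 | 0.804 | 0.095 |
| 30% | 0.494 | 0.634 | 0.140 |
| 40% | 0.309 | 0.464 | 0.154 |
| 50% | 0.172 | 0.313 | 0.141 |

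**3. Size averaged over how often it happens.** The documents give no pre-alvocidib stopping rate *d*; I assume 5% to 20%. If every patient, including those added, independently stops early with probability *d* and is scored as a non-event, *p* becomes q = p(1−d) in the all-exposed formula. At p = 0.30:

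- d = 5%: q = 0.285, P(pass) = 0.525
- d = 20%: q = 0.240, P(pass) = 0.622
- reference, d = 0: 0.494

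The chance that at least one of three is unexposed, 1 − (1−d)³, runs from 0.143 to 0.488 over that range.

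**4. MTD criterion (at most 1 DLT in 6).** If only five of the six are exposed, the chance of meeting it at p = 0.30 is 0.7⁵ + 5 × 0.3 × 0.7⁴ = 0.528, against 0.7⁶ + 6 × 0.3 × 0.7⁵ = 0.420.

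**5. Reporting.** As a hypothetical, take one DLT and one unexposed patient. A cohort of three shows 1/3 (33%) on the SAP set and 1/2 (50%) among exposed patients; a cohort of four shows 1/4 (25%) and 1/3 (33%).

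**The case against.** Four stronger readings are tempting, and the documents do not support them.

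- **That such a patient does count as DLT-free.** No passage says so. The protocol's cohort and committee wording leans towards alvocidib-treated patients. The Safety set is the population for tables; nothing makes it the denominator for escalation decisions.
- **That only never-dosed patients are replaceable.** This requires 'study drug' in SAP Section 5 to include DEC and AZA. If it means alvocidib, a patient lost or withdrawing consent before Day 8 or 10 may be replaced. The Phase 2 rule also allows replacement of dosed patients, though only for response.
- **That four patients in Cohorts 4 and 6 reveals a denominator problem.** Protocol Section 4.1 allows cohorts of 3-6 and up to three additions, so four is a permitted size. The documents do not explain it.
- **That this SAP text will pass toxic doses.** Sites were told of closure on 17 November 2020, with 20 Phase 1b patients enrolled and none in expansion or Phase 2. No escalation decision remains.

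Two further objections are fair. The DLT criteria mostly speak of drug-related, not alvocidib-related, toxicity, so an early DEC or AZA event could qualify; the figures assume none does. And the tables listed in SAP Sections 12.1 and 12.2 include no DLT-rate table.

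What survives is the missing definition, the conflict between the Safety sets and the unclear replacement term. The absence of a listed DLT table does not help: DLTs and the MTD remain safety endpoints to be reported, with no proper denominator specified.

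**Conclusion.** The point holds as a gap and a conflict, not as a demonstrated error in any cohort. A reader following the SAP could put a patient given only DEC or AZA in the DLT denominator; a reader following the protocol's Safety set would not.

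Conditional on one such patient among the first three, and no DLT before alvocidib, a dose passes about 4 to 15 percentage points more often across assumed DLT rates of 10% to 50%. The averaged effect at a 30% rate is smaller, about 3 to 13 points over the assumed stopping rates. Both ranges rest on rates the documents do not give, and neither covers exposed patients who leave before the end of Cycle 1.

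These figures show how sensitive the 3+3 rule is to the definition; they do not predict what happened. The remaining consequence is for the synoptic report: whether DLT counts, and any MTD statement, rest on patients who received the dose in question.

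**What to change.** In the SAP:

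1. Define a DLT-evaluable set: patients who received Cycle 1 alvocidib and either had a DLT or completed the DLT window. State the window length. Protocol Section 4.5.3 says Cycle 1 and the escalation condition uses Day 28, yet two DLT criteria need about 42 days; those passages must be reconciled.
2. Report DLTs per cohort, and any MTD statement, on that set.
3. List each non-evaluable patient, the reason, and how that patient was treated in the escalation decision for the cohort. Show separately any DLT-type event before alvocidib.
4. Reconcile the SAP and protocol Safety sets and record the change in SAP Section 16. The same entry should cover treatment emergence, which starts at first alvocidib in Protocol Section 11.10.1 and at first study drug in SAP Section 12.1.
5. State what 'study drug' means in the SAP Section 5 replacement rule.

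Keep the any-treatment set for general adverse event tables, where events after DEC or AZA belong.

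The cost is a few sentences in the SAP and a re-cut of 20 patients, with slightly smaller DLT denominators if any patient proves non-evaluable. No new data or patients are needed.
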